**CONFIDENTIAL**

---

**Protocol Summary.** Following a thorough review of the patient's health history, clinical and radiographic examination, qualified subjects will sign an informed consent to be enrolled in the study. Treatment will be randomly assigned to quadrants and implemented according to the following standardized protocol:

1. Participants will be provided with oral hygiene aids and receive standardized oral hygiene instructions.
2. One week following oral hygiene instruction participants will return for collection of baseline clinical data including:
  - a. Plaque index
  - b. Gingival index
  - c. Bleeding on probing
  - d. Probing pocket depth
  - e. Gingival recession
  - f. Clinical attachment levels (calculated)
3. Each qualifying quadrant will be randomly assigned to scaling and root planing alone or scaling and root planing with adjunctive laser treatment.
4. At the time of treatment, occlusal contacts will be evaluated and appropriate occlusal adjustments will be made if deemed necessary (i.e. adjustment of occlusal interferences and/or fremitus).
5. Each quadrant will be treated, according to assigned group, at separate visits that are at least two weeks apart.
6. A plaque sample (biofilm) will be collected from selected sites in each qualifying quadrant prior to treatment for microbial analysis. This will be repeated at the re-evaluation appointments.
7. A visual analog scale will be used to assess pain during the first 24-48 hours.
8. Subjects will keep a log of the type and amount of analgesics taken.
9. Subjects will be evaluated at 3, 6, 9 and 12 months after therapy.
10. Periodontal recall maintenance will be provided, as needed, at 3, 6, 9 and 12 months. Oral hygiene instructions will be reinforced at each visit.

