**Inclusion criteria**

- Age 18 years old or older (male or female)
- Healthy without systemic diseases that may adversely effect healing
- Not pregnant and no current plans to become pregnant
- No periodontal treatment in the previous 6 months
- No systemic antibiotic therapy in the previous 6 months
- At least two quadrants with chronic periodontitis (ideally opposite side same jaw)
- Each quadrant must have two or more sites with probing pocket depths  $\geq 5$ mm
- Presence of interproximal intrabony defect(s) in each quadrant

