**CONFIDENTIAL**

- 
11. Radiographic imaging (intraoral digital periapical radiograph and cone beam computed tomography scan) will be taken of each quadrant/treatment site at baseline, 6 and 12 months.
  12. Subjects will complete a written survey to answer questions about their satisfaction with the treatment provided.

**Treatment Groups.** Each subject must have at least two qualifying quadrants. One quadrant will be randomly assigned to one of the two treatment groups (control or test) and the second quadrant will be assigned to the other group. Every subject will have at least one quadrant assigned to the control group and one quadrant assigned to the test group and will thus serve as their own control. Each additional qualifying quadrant in the same individual will be assigned to the next treatment group (i.e. if the second quadrant was assigned to the test group, then the third quadrant will be assigned to the control group and the fourth quadrant will be assigned to the test group). Treatment of multiple quadrants in the same group for the same subject will be treated on the same visit in order to maintain a reasonable follow-up / data collection schedule. All treatment will be completed with local anesthesia.

Group 1 (control):

- Non-surgical, mechanical scaling and root planing with hand instruments and ultrasonic device.

Group 2 (test):

- Non-surgical, mechanical scaling and root planing with hand instruments and ultrasonic device including the use of adjunctive WaterLase iPlus (Er,Cr:YSGG) laser therapy according to the following REPAIR protocol. See Attachment 1.

**Post-treatment Instructions.** All patients will be provided with specific oral hygiene instructions. From day two until day seven, patients will be instructed to brush with a

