**CONFIDENTIAL**

---

manual soft or extra-soft toothbrush and to use interproximal cleaning aids. Patients will return for postoperative evaluation at week 2 and months 1, 3, 6, 9 and 12.

**Recall Maintenance Cleanings.** Supportive periodontal therapy (recall maintenance cleanings) will be completed, as needed, at 3, 6, 9, and 12 months after treatment. Recall maintenance therapy will be limited to supragingival scaling and prophylaxis.

**Data Collection.** Data will be collected in a standardized, de-identified fashion and will be stored in a locked file cabinet at the study site. Data will be entered into a password-protected database. At the completion of the study including analysis and publication, the data sheets will be destroyed.

**Clinical Measurements.** The following clinical measurements will be recorded at the initial baseline examination (0), 3, 6, 9, and 12 months after treatment:

- Probing depth (PD) at six sites for each tooth
- Bleeding on probing (BOP) at six sites for each tooth
- Plaque index (PI) at six sites for each tooth
- Gingival index (GI) at six sites for each tooth
- Gingival recession at six sites for each tooth
- Clinical attachment level (CAL) at six sites for each tooth (calculated)
- Plaque score % (calculated)
- Bleeding score % (calculated)

**Data Analysis.** A biostatistician will be consulted for data analysis. Comparative evaluation of radiographic imaging will be analyzed with an experienced consultant.

**Patient Compensation.** Subjects will not receive financial compensation for participation in this study. Subjects will be provided with non-surgical periodontal treatment including laser therapy as well as 1 year post-initial therapy maintenance associated with the study at no cost to them. Periodontal therapy will include scaling

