**CONFIDENTIAL****ATTACHMENT 1****REPaIR Protocol (Regenerative, Er,Cr:YSGG, Periodontitis, ai, Regimen)**

- 1) Surgical preparation: Following patient identification, review of health history and checking vital signs, local anesthesia is applied to the area.
- 2) Outer pocket de-epithelialization: The outer pocket gingival epithelium is removed (and gingivectomy performed if pseudopocket) with laser. Setting: RFTP5, 1.5W, 15% air, 15% water, 30 Hz, H mode (iPlus preset).
- 3) De-epithelialization and retraction: The inner pocket epithelium is removed from the free gingival margin to the level equal with the pocket depth. Setting: MZ6, 1.5W, 11% air, 20% water, 30 Hz, H mode (iPlus preset).
- 4) Scaling and Root Planing: Conventional treatment with hand instruments and ultrasonics to remove root surface accretions /calculus, and to smooth root surface cementum/dentin.
- 5) Sulcular Debridement / Degranulation: The purpose of this step is to remove smear layer from root surface, to completely remove pocket lining and to degranulate the pocket. Setting: RFPT5, 1.5W, 20% air, 40% water, 30 Hz, H mode (iPlus preset).
- 6) Bone Decortication: The purpose of this step is to recontour osseous defects and to stimulate bone regeneration. The tip is held parallel to the root surface while gently tapping all the way down to bone at the base of the defect. The laser slightly penetrates the bone at each point as this step is repeated stepwise around the tooth. The angle of the tip maybe changed to treat the walls of the intrabony defect. Setting: MZ6, 2.5W, 70% air, 80% water, 30 Hz, H mode (iPlus preset).
- 7) Sulcular Debridement: The purpose of this step is to remove the residual debris while inducing blood coagulation. The laser tip is gently brushed through the entire periodontal pocket in a sweeping motion from the base to the top of the pocket. Setting: RFPT5, 1.5W, 10% air, 10% water, 30 Hz, H mode (iPlus preset).
- 8) Compress: The surgical site is compressed with moistened 2 x 2 gauze using finger pressure for five minutes to achieve hemostasis.
- ~~9) *Optional -Biostimulation: Application of the 940nm diode laser with pain therapy handpiece. Setting: 3.0W for 30 seconds directed toward the apices and another 30 seconds directed toward the gingival margins. THIS OPTIONAL STEP WILL NOT BE INCLUDED IN THIS STUDY— CONSIDER FOR FUTURE STUDIES.*~~

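### Occlusal adjustment is decided at a treatment visit that belongs to one arm, so a discretionary co-intervention could differ between arms

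*Combined protocol and SAP*

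**What the plan says.** The Protocol Summary sets the order of events. Baseline clinical data are collected in step 2, and the list there has no occlusal item. Quadrants are assigned in step 3. Step 4, which is timed to the treatment visit, then states that "occlusal contacts will be evaluated and appropriate occlusal adjustments will be made if deemed necessary (i.e. adjustment of occlusal interferences and/or fremitus". Step 5 adds: "Each quadrant will be treated, according to assigned group, at separate visits that are at least two weeks apart".

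For patients with more than two qualifying quadrants, Treatment Groups states that "Treatment of multiple quadrants in the same group for the same subject will be treated on the same visit". Each treatment visit therefore still belongs to one arm.

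The test treatment uses the laser at several stages, beginning with step 2 of Attachment 1: "The outer pocket gingival epithelium is removed (and gingivectomy performed if pseudopocket) with laser".

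The Inclusion criteria give a preferred position for the quadrants but do not require it: "At least two quadrants with chronic periodontitis (ideally opposite side same jaw".

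The recorded variables under Clinical Measurements start with "Probing depth (PD) at six sites for each tooth" and go on to bleeding, plaque and gingival indices, recession, attachment level and two summary scores. Occlusal adjustment is not among them. Data Analysis says only that a biostatistician will be consulted.

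**The concern.** Randomising quadrants within a patient balances the need for occlusal adjustment on average. It does not balance decisions made afterwards by someone who knows which arm is being treated. Step 4 leaves the decision to judgement. Interferences and fremitus are named as targets, but no threshold is set. The text does not say who decides or when the allocation is revealed. However, the visit is devoted to one arm and only one arm uses a laser, so the operator would very likely know.

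If adjustment is done more often in one arm and affects the outcome, the within-patient difference mixes the laser effect with the adjustment effect. The split-mouth design removes differences between patients. It does not remove a co-intervention that differs between quadrants of the same mouth. With no record specified, the plan does not ensure that an imbalance could be detected, described or allowed for.

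There is a related, smaller point. Where opposing quadrants are in different arms, one adjustment could affect both. This does not arise in a two-quadrant patient with the preferred same-jaw pair.

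**Working it through.** **Order of events.** Reading steps 2 to 5 in sequence gives: baseline data without occlusion, then assignment, then occlusal evaluation at the time of treatment, with treatment by assigned group at separate visits. The rule for multiple quadrants keeps each visit within one arm. As written, the adjustment decision therefore falls after assignment and inside an arm-specific visit.

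**Formula.** For a quadrant-mean outcome:

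bias = (difference in adjustment rate between arms) × (effect per adjusted tooth) × (adjusted teeth ÷ teeth per quadrant)

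The bias is zero only if the rates are equal or adjustment has no effect.

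**Inputs.** The only planning figure in the documents is 35 patients (Materials and Methods). No power calculation is given, so there is no planned detectable difference to reproduce. Everything else is assumed:
- quadrant mean as the outcome, with seven teeth per quadrant
- one or two teeth adjusted
- an effect of 0.5 to 1 mm on each adjusted tooth
- adjustment 10 to 30 percentage points more frequent in one arm
- SD of the within-patient difference 0.8 mm, varied to 0.6 and 1.0 mm
- two-sided 5% paired t-test, all 35 patients analysed (34 degrees of freedom)

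**Bias.**
- Low: 0.10 × 0.5 × 1/7 = 0.007 mm
- Middle: 0.20 × 0.75 × 1.5/7 = 0.032 mm
- High: 0.30 × 1.0 × 2/7 = 0.086 mm

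**Detectable difference.** From the noncentral t distribution, 80% power with n = 35 needs a difference of 0.487 × SD. At SD 0.8 mm this is 0.487 × 0.8 = 0.39 mm. The bias is then 0.007/0.39 = 2% of it at the low end and 0.086/0.39 = 22% at the high end.

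**Rejection rate when the laser has no effect.** The noncentrality is bias × √35 ÷ SD. In the high case at SD 0.8 mm it is 0.0857 × 5.916 ÷ 0.8 = 0.634.

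| Case | SD (mm) | Rejection rate |
|---|---|---|
| Low | 0.8 | 5.0% |
| Middle | 0.8 | 5.6% |
| High | 0.8 | 9.4% |
| High | 0.6 | 13.0% |
| High | 1.0 | 7.8% |

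**The case against.** The strongest reply is that this is a possibility and not an error. One rule with a named indication applies to both arms, and randomisation balances the underlying need. A difference arises only if the operator applies that rule differently because the arm is known, and nothing in the documents suggests so. Much the same remark could be made of any unmasked device trial that allows indicated care. This stands as a limit on severity. It does not remove the concern, because the plan does nothing to ensure equal use and a simple change would.

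Four further points carry some weight.
- Step 4 does not say whether the evaluation covers the whole mouth or only the quadrant being treated, or whether it is repeated at each visit. A whole-mouth adjustment at the first visit would reach both arms and dilute the contrast. It would also fall before treatment for one arm and after treatment for the other.
- The lack of a log is inferred from silence. Clinical Measurements lists outcomes, and the data sheets are not in the documents. It is fair to say that no record is specified. It would not be fair to say that none would be kept.
- The upper false-positive figures need every assumption at its maximum together. At mid-range values the rate is about 5.6%.
- The remedy still allows unplanned adjustments at the treatment visit. These would be visible but not prevented.

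**Conclusion.** The concern holds as a minor point. The plan places a discretionary co-intervention after assignment, at visits that each belong to one arm, with no operator masking, threshold or adjustment record specified. Its use could therefore differ between arms and be read as a laser effect. That conclusion rests on the text alone and does not depend on the arithmetic.

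The direction cannot be determined and the size is probably small. The calculated range is only illustrative, because the adjustment rate, its effect, the SD, the outcome summary and the test are all assumed. It should not be taken as evidence that harm will occur. The case for acting is that the protection costs very little.

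**What to change.** Reword step 4 so that occlusion is evaluated for every qualifying quadrant at the baseline data visit, and the decision to adjust is recorded before the allocation is opened. The adjustment itself can still be made at the treatment visit. Log every adjustment by tooth, quadrant and date, including any not planned at baseline, and report the counts by arm. The clinical criteria for adjusting remain with the investigators.

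The cost is one reworded step, one line on the data sheet and a few extra minutes at a visit that already takes place. No additional visits or patients are needed.

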**CONFIDENTIAL**

- 
11. Radiographic imaging (intraoral digital periapical radiograph and cone beam computed tomography scan) will be taken of each quadrant/treatment site at baseline, 6 and 12 months.
  12. Subjects will complete a written survey to answer questions about their satisfaction with the treatment provided.

**Treatment Groups.** Each subject must have at least two qualifying quadrants. One quadrant will be randomly assigned to one of the two treatment groups (control or test) and the second quadrant will be assigned to the other group. Every subject will have at least one quadrant assigned to the control group and one quadrant assigned to the test group and will thus serve as their own control. Each additional qualifying quadrant in the same individual will be assigned to the next treatment group (i.e. if the second quadrant was assigned to the test group, then the third quadrant will be assigned to the control group and the fourth quadrant will be assigned to the test group). Treatment of multiple quadrants in the same group for the same subject will be treated on the same visit in order to maintain a reasonable follow-up / data collection schedule. All treatment will be completed with local anesthesia.

Group 1 (control):

- Non-surgical, mechanical scaling and root planing with hand instruments and ultrasonic device.

Group 2 (test):

- Non-surgical, mechanical scaling and root planing with hand instruments and ultrasonic device including the use of adjunctive WaterLase iPlus (Er,Cr:YSGG) laser therapy according to the following REPAIR protocol. See Attachment 1.

**Post-treatment Instructions.** All patients will be provided with specific oral hygiene instructions. From day two until day seven, patients will be instructed to brush with a

**CONFIDENTIAL**

---

manual soft or extra-soft toothbrush and to use interproximal cleaning aids. Patients will return for postoperative evaluation at week 2 and months 1, 3, 6, 9 and 12.

**Recall Maintenance Cleanings.** Supportive periodontal therapy (recall maintenance cleanings) will be completed, as needed, at 3, 6, 9, and 12 months after treatment. Recall maintenance therapy will be limited to supragingival scaling and prophylaxis.

**Data Collection.** Data will be collected in a standardized, de-identified fashion and will be stored in a locked file cabinet at the study site. Data will be entered into a password-protected database. At the completion of the study including analysis and publication, the data sheets will be destroyed.

**Clinical Measurements.** The following clinical measurements will be recorded at the initial baseline examination (0), 3, 6, 9, and 12 months after treatment:

- Probing depth (PD) at six sites for each tooth
- Bleeding on probing (BOP) at six sites for each tooth
- Plaque index (PI) at six sites for each tooth
- Gingival index (GI) at six sites for each tooth
- Gingival recession at six sites for each tooth
- Clinical attachment level (CAL) at six sites for each tooth (calculated)
- Plaque score % (calculated)
- Bleeding score % (calculated)

**Data Analysis.** A biostatistician will be consulted for data analysis. Comparative evaluation of radiographic imaging will be analyzed with an experienced consultant.

**Patient Compensation.** Subjects will not receive financial compensation for participation in this study. Subjects will be provided with non-surgical periodontal treatment including laser therapy as well as 1 year post-initial therapy maintenance associated with the study at no cost to them. Periodontal therapy will include scaling

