**CONFIDENTIAL**

---

**Instrumentation.** The laser to be used in this protocol is the Waterlase iPlus Er,Cr:YSGG laser manufactured by Biolase (Irvine, California, USA).

Laser specifications as described by the manufacturer:

- Model: Waterlase iPlus
- Operating Voltage: 100 VAC  $\pm$  10% / 230VAC  $\pm$  10%
- Frequency: 50 / 60 Hz
- Current Rating: 15.0 A / 8A
- Laser classification: Class 4 (Er,Cr:YSGG), Class 1 (635nm red Aiming Beam)
- Type of laser: Er,Cr:YSGG
- Wavelength: 2780 nm
- Type of operation: Pulse
- Laser energy: 0- -600 mJ
- Aiming Beam: 635nm (red)
- Cooling method: Water cooling (built-in reservoir)
- Outer dimensions (WxDxH): 11" x 19" x 33" (246mm x 585mm x 1057mm)
- Weight: Approx. 75 lb. (34 kg)

**Operator training.** A training session offered by Biolase and The World Congress for Laser Instruction (WCLI) for the use of the Waterlase iPlus Er,Cr:YSGG laser has been completed by the principal investigator and will be completed by all co-investigators participating in this study.

A pressure sensitive Florida Probe will be used to standardize and calibrate examiners. A UNC-15 periodontal probe will also be used in this study to evaluate the clinical parameters. It has markings in 1 mm increments up to 15 mm.

Non-surgical instrumentation will include the use of a Symmetry IQ 3000 Piezo Scaler (Hu-Friedy) with fiber optic light and various tips, Universal and Gracey curettes (Hu-Friedy).

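### The available text does not mask follow-up examiners or image readers to quadrant assignment, so a reading lean tied to known assignment would pass one-for-one into the laser-minus-control difference

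*Combined protocol and SAP*

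**What the plan says.** All places are in the combined protocol and SAP, Materials and Methods.

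- **Design.** Under Treatment Groups, "Every subject will have at least one quadrant assigned to the control group and one quadrant assigned to the test group", so the comparison is made within the patient.
- **Order of baseline and assignment.** Protocol Summary item 2: "One week following oral hygiene instruction participants will return for collection of baseline clinical data". Item 3 follows: "Each qualifying quadrant will be randomly assigned to scaling and root planing alone or scaling and root planing with adjunctive laser treatment".
- **Clinical readings.** Under Clinical Measurements, "The following clinical measurements will be recorded at the initial baseline examination (0), 3, 6, 9, and 12 months after treatment". The list holds probing depth, bleeding, plaque index, gingival index and recession at six sites per tooth, with attachment level calculated. The Abstract adds a 1-month measurement.
- **Images.** Protocol Summary item 11 schedules periapical and cone beam images at baseline, 6 and 12 months. It does not say when they are read. Data Analysis says: "Comparative evaluation of radiographic imaging will be analyzed with an experienced consultant".
- **Nearest safeguards.** "A pressure sensitive Florida Probe will be used to standardize and calibrate examiners" (end of Operator training) and "Data will be collected in a standardized, de-identified fashion" (Data Collection).
- **People.** Laser training "has been completed by the principal investigator and will be completed by all co-investigators participating in this study" (Operator training). Nobody is named as reserved for examination.

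No available section states masking of examiners or image readers, separation of examiner from operator, or coding of images by arm or time point. Some pages were removed from the public text, including material just before Materials and Methods. The statement is therefore limited to what is available.

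**The concern.** Both Specific Aims rest on readings that involve judgement: clinical parameters for disease resolution, and bone levels on images as the surrogate for regeneration. The sections where masking would normally appear (instrumentation, calibration, assignment, measurement, data handling, image analysis) are present and silent on it.

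The provisions that are there do other jobs. Calibration limits differences between examiners. De-identification protects the patient's identity, not the arm. The consultant's experience is a qualification, and analysing images together with a consultant leaves open who actually reads them.

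Split-mouth pairing removes what the two quadrants share, and knowledge of assignment is not shared between them. A lean toward the lasered quadrant could create an apparent benefit, and a lean against it could hide a real one. Neither pairing nor more patients corrects this, and masking cannot be added after the readings have been made.

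**Working it through.** **1. Which readings are exposed.** Items 2 and 3 of the Protocol Summary place clinical baseline collection before assignment, so baseline clinical readings appear to be protected by their order. That order does not carry over to images. Item 11 gives the time when baseline images are taken, not when they are read, and they may be read after assignment. The exposed readings are therefore the follow-up clinical measurements and all images, baseline included.

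**2. How a lean transfers.** Let L and C be the true values in a patient's laser and control quadrants, and let bL and bC be the assessor's leans on each. The expected observed difference is

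E[(L + bL) − (C + bC)] = (true difference) + (bL − bC).

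| Lean on laser (mm) | Lean on control (mm) | Shift in the difference (mm) |
|---|---|---|
| +0.3 | 0 | +0.30 |
| 0 | −0.3 | +0.30 |
| +0.15 | −0.15 | +0.30 |
| −0.3 | 0 | −0.30 |
| +0.3 | +0.3 | 0.00 |

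Only the differential part survives, and it survives in full. The number of patients does not enter the formula.

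**3. Scale, as illustration only.** The plan states no test, alpha, SD, expected benefit or power, so it offers no figure to reproduce. The one input taken from it is the 35 patients. Assumed: one pair per patient, a two-sided 5% paired t-test, a paired SD of 0.6, 0.8, 1.0 or 1.5 mm, and a net lean b in probing depth. With no true effect the test statistic is noncentral t on 34 df with noncentrality b × √35 / SD, where √35 = 5.916. For b = 0.1 mm the noncentralities are 0.1 × 5.916 / 0.6 = 0.986, then 0.740, 0.592 and 0.394. The critical value is 2.032. False-positive rates:

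| Net lean | SD 0.6 | SD 0.8 | SD 1.0 | SD 1.5 |
|---|---|---|---|---|
| 0.02 mm | 5.4% | 5.2% | 5.2% | 5.1% |
| 0.05 mm | 7.7% | 6.5% | 6.0% | 5.4% |
| 0.1 mm | 16.0% | 11.1% | 8.9% | 6.7% |
| 0.2 mm | 48.3% | 30.1% | 21.0% | 12.0% |

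In the other direction, take an assumed true benefit of 0.4 mm. Power without a lean is 97%, 82%, 63% and 33.5% across the four SDs. A 0.1 mm lean against the laser leaves a net 0.3 mm, and power becomes 82%, 58%, 41% and 21%.

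**4. What this does not cover.** The documents give no basis for the size of lean to expect. The table concerns probing depth only; bleeding, plaque index, gingival index and imaging are not quantified.

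**The case against.** The strongest reply is that this is silence, not a decision to assess unmasked. Masking may be described in removed pages or simply done in practice. That stands as a limit on the claim, but it does not answer the point: a team following the available text has no masking rule to follow. If masking is already intended, writing it down costs almost nothing.

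A second reply is that the illustration rests on assumed inputs and runs from about 5% to 48%, so it cannot show whether the problem is small or large here. That is correct, and very small leans matter little. The conclusion rests on the transfer in step 2, which needs none of those inputs.

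A third is that masking may fail in any case. Attachment 1, step 2 (outer de-epithelialization, gingivectomy where there is a pseudopocket) and step 6 (bone decortication) may leave visible signs. The documents do not say whether these persist to the first follow-up measurement or to the 6- and 12-month images. Imperfect masking is a limitation to report, not a reason to specify none.

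A reader might also infer three stronger things that the documents do not support:

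- *That any tendency to read high or low biases the result.* A tendency common to both quadrants cancels within the patient.
- *That the treating operator will do the examining.* Training every investigator on the laser does not show this. The plan speaks separately of examiners and does not say who they are.
- *That the results will be biased, or biased toward the laser.* Nothing establishes that a lean exists or which way it would run.

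**Conclusion.** The concern holds in this form. The available text does not mask follow-up clinical examiners, or the readers of any image, to quadrant assignment, and the safeguards it does contain do not hide which quadrant was lasered. An assignment-related lean would enter the treatment difference in full, in either direction, at any sample size. This is exposure to bias, not a finding that bias occurred.

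The size is unknown. Under the stated assumptions (35 pairs, two-sided 5% paired t-test, paired SD 0.6 to 1.5 mm), a 0.1 mm lean in probing raises the false-positive rate from 5% to between 7% and 16%. The team should make the change because it protects both aims at low cost. Confidence is medium, because part of the document could not be read and the size of any lean is not known.

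**What to change.** Add two rules under Clinical Measurements and Data Analysis.

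**(a) Images.** All periapical and cone beam images, baseline included, are coded by existing staff who do not read them. They are read in random time order by readers masked to arm, meaning the consultant and any investigator who measures.

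**(b) Follow-up clinical measurements.** Whatever the staffing, the allocation and treatment record are kept off the follow-up measurement form and are not consulted before the measurements are recorded. Patients are asked not to tell the examiner which quadrant was lasered. Where existing staffing allows, the examiner is a calibrated investigator who did not treat that patient.

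Record who examined at each visit and who read each image, and report where separation was not possible.

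**Cost.** Coding covers at least 35 patients × 2 quadrants × 3 time points = 210 quadrant-time image assessments per modality. There is also some scheduling work and an identity field on the forms. The rules themselves call for no additional reader. The number of investigators is not given, so operator-examiner separation may be only partial; the recorded identities would show how often it was achieved. Masking may remain imperfect if soft-tissue or bone changes from the laser steps are visible.
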